6.7 Sample Size

Assumptions

- Outcome	: Pain score
- Standard deviation (σ)	: 1.81
- Clinically meaningful margin (Δ or δ)	: 1.0
- Power	: 80% ($Z_{1-\beta} = 0.84$)
- Significance level (α)	: 0.05

Reference standard deviation from Kocak AO, Dogruyol S, Akbas I, Menekse TS, Gur STA, Kocak MB, Cekmen B, Orun S, Cakir Z. Comparison of topical capsaicin and topical piroxicam in the treatment of acute trauma-induced pain: A randomized double-blind trial. Am J Emerg Med. 2020 Sep;38(9):1767-1771. doi: 10.1016/j.ajem.2020.05.104. Epub 2020 Jun 2. PMID: 32739846.

For **equivalence trials with 3 groups**, you typically plan for **pairwise equivalence testing**:

- Diclofenac vs. Piroxicam
- Diclofenac vs. PXM plus Counterirritant
- Piroxicam vs. PXM plus Counterirritant

This means you must **adjust α** to account for **multiple comparisons**, commonly using **Bonferroni correction**:

$$\text{Adjusted } \alpha = 0.05 / 3 = 0.0167 \rightarrow Z_{1-\alpha/2} \approx \mathbf{2.39}$$

Sample Size Formula and Calculation

Using the formula for equivalence trials:

$$n = ((Z_{1-\alpha/2} + Z_{1-\beta}) \times \sigma / \Delta)^2$$

Substituting the values:

$$n = ((2.39 + 0.84) \times 1.81 / 1.0)^2$$

$$n = (4.059 \times 1.81)^2 = (7.35)^2 = 54.0$$

Sample size per group (rounded): 54

Total sample size for 3 groups: 162

With 10% dropout:

Total = $162 / (1 - 0.10) \approx 180$ participants

Recommended: 60 participants per group

The clinical study will be recruited in total 180 subjects, which means 60 subjects per arm.

Justification:

- We used the reference from Kocak et al. because: The study used topical piroxicam, which is the main active ingredient in Counterpain PXM. The study was randomized, double-blind, and controlled, and reported the standard deviation of pain scores in full—a parameter that is essential for sample size calculations. To date, we have not found any publications comparing diclofenac gel directly with topical piroxicam, with standard deviations appropriate for use in statistical calculations. So, even though the comparator was capsaicin, this reference was chosen because it is quite representative in terms of pain type and study design.

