7.9.1 Primary Endpoint

The assessment of primary endpoint will be assessed through form 2, Inventerisasi Rasa Nyeri Singkat on 1st Visit, 2nd Visit and 3rd Visit.

The primary end-point is the difference BPI scale ≥ 3 , from initial scale of pain to the end of treatment will be captured as the primary efficacy endpoint.

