7.10 STATISTICAL ANALYSIS

7.4.1 Analysis Sets

In the efficacy analysis, the **Per Protocol Set (PPS)** will be used as the primary analysis set, while the **Full Analysis Set (FAS)** will serve as the secondary analysis set. For safety analysis, the **Safety Analysis Set** will be used. The definitions are as follows:

- **Per Protocol Set (PPS):**
The PPS includes participants who do not have any major protocol violations (such as not meeting inclusion/exclusion criteria or poor compliance), and who have completed the required assessments of the primary endpoint as specified in the protocol.
- **Full Analysis Set (FAS):**
The FAS includes all participants who received at least one dose of the study drug and had at least one post-baseline assessment for efficacy endpoints. This set reflects the intention-to-treat principle.
- **Safety Analysis Set:**
The Safety Analysis Set includes all participants who received at least one dose of the study drug and had at least one post-baseline safety assessment. All safety data, including adverse events and rescue medication use, will be analyzed in this set.

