7.4.2 Statistical Analysis Plan

The statistical analysis will be performed after data finalization and database lock, following the predefined analysis sets (PPS, FAS, and Safety Analysis Set). All analyses will be conducted using standard statistical software (e.g., SPSS, SAS, or R), with the level of statistical significance set at $p < 0.05$, unless otherwise adjusted.

Efficacy Analysis

- **Primary Endpoint (Pain Score using Brief Pain Inventory):**
 - **Test: Analysis of Covariance (ANCOVA)** adjusting for baseline BPI score

- **Equivalence testing:** Pairwise comparisons using **two one-sided t-tests (TOST)** to assess whether the difference in mean change from baseline falls within the equivalence margin (± 1.0)
- **Assumptions:** Normality and homogeneity of variance will be checked. If violated, non-parametric equivalent (e.g., **Wilcoxon rank-sum test**) will be used.
- **Secondary Endpoints:**
 - **Range of Motion (ROM) and Muscle Strength:**
 - **Test:** Repeated Measures ANOVA or mixed-effects model, depending on data completeness and correlation structure
 - If non-normal: **Friedman test** or **Wilcoxon signed-rank test** for within-group, **Kruskal-Wallis test** for between-group comparisons.
 - **Thermal Sensation, Comfort, and Acceptance (ASHRAE Scale):**
 - **Test:** Chi-square test or Fisher's exact test for categorical comparisons
 - **Ordinal regression** may be used to explore patterns of thermal perception across groups.
 - **Responding Analysis (pain reduction ≥ 3 points):**
 - **Test:** Chi-square test for group-wise comparison of response rates
 - **Risk difference** and **number needed to treat (NNT)** will be calculated.

Safety Analysis

- **Adverse Events (AEs) and Adverse Drug Reactions (ADRs):**
 - **Test:** Chi-square test or Fisher's exact test for comparing incidence across groups
 - Descriptive statistics for type, severity, onset, and duration
 - **Severity grading** and **causality assessment** using **Naranjo's algorithm**.
- **Rescue Medication Use:**
 - **Test:** Poisson regression or negative binomial regression if data are overdispersed
 - Summarized as a mean number of doses used per participant and compared between groups.

Demographic and Baseline Characteristics

- **Continuous Variables** (e.g., age, BMI):
 - **Test:** One-way ANOVA or **Kruskal-Wallis test** (if non-normal distribution)
- **Categorical Variables** (e.g., sex, diagnosis):
 - **Test:** Chi-square test or Fisher's exact test as appropriate

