
Missing Data Handling

- **Primary Analysis** will be based on the **Per Protocol Set**, with sensitivity analysis using **Full Analysis Set (FAS)** under **intention-to-treat (ITT)** principles.
- **Multiple imputation** will be considered for missing primary endpoint data if the proportion of missing data exceeds 5%.

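### The 5% imputation rule cannot act in the per-protocol primary analysis and commits to nothing in the FAS, the only planned sensitivity analysis

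*Protocol*

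**What the plan says.** Section 7.4.1 makes the Per Protocol Set (PPS) primary for efficacy. Besides having no major violation, its members must be those "who have completed the required assessments of the primary endpoint as specified in the protocol". The FAS is secondary and takes participants who "received at least one dose of the study drug and had at least one post-baseline assessment for efficacy endpoints". A FAS member can therefore lack the end-of-treatment score.

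Under Missing Data Handling, section 7.4.2 bases the primary analysis on the PPS, "with sensitivity analysis using Full Analysis Set (FAS) under intention-to-treat (ITT) principles". It then says that multiple imputation "will be considered for missing primary endpoint data if the proportion of missing data exceeds 5" per cent. The section says nothing else about missing data.

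The same section plans an ANCOVA adjusted for baseline BPI and pairwise TOST of whether the "difference in mean change from baseline falls within the equivalence margin" of ±1.0. Section 7.9.1 collects the BPI form, "Inventerisasi Rasa Nyeri Singkat on 1st Visit, 2nd Visit and 3rd Visit". Section 6.7 sizes the trial at 180, 60 per arm, "With 10% dropout". Section 7.8.1 lists worsening of the target disease and adverse events among the reasons for discontinuation. Section 7.8.2 asks for the scheduled observations and tests when a participant discontinues.

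**The concern.** The concern is the imputation rule itself, not the choice of the PPS as primary set.

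In an equivalence trial, losing non-responders from a weaker or more irritating gel moves that arm's observed mean towards the others, and so towards a false claim of equivalence. The PPS is exposed to this by construction. The FAS is the one analysis that could reveal it, but only if it makes proper use of participants who left before the end.

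The rule does not secure that. Above the threshold the analyst may impute or not, and can decide after seeing the data. At or below it nothing is specified. The threshold is a bare proportion, whereas bias in a pairwise difference depends on how missingness is split between the two arms and on why participants left. If the FAS ends up using only those with a final BPI, it shares the PPS's loss, and agreement between the two sets gives little reassurance.

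**Working it through.** **1. Where the rule can act.** PPS membership requires completed primary assessments, so missing primary data in the PPS are 0% by definition and the 5% trigger is never reached there. FAS membership requires one dose and one post-baseline efficacy assessment, so the final BPI can be missing. The rule is live only in the FAS.

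**2. What it does there.** Above 5%, imputation is optional. At or below 5%, no method is given. The analysis set and denominator for the 5% are not stated.

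**3. The plan's own figures.** The Protocol gives no figure for missing-data bias. Its dropout inflation reproduces: 162 / (1 − 0.10) = 180, or 60 per arm. Counted over all participants, 0.05 × 180 = 9, so up to 9 missing would not exceed the trigger.

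**4. Illustration of size.**
- From the Protocol: 60 per arm, margin 1.0, SD 1.81 (section 6.7).
- Assumed: leavers did *d* = 1.5 to 3 points worse than those observed in the same arm; the true difference lies exactly at the margin; the analysis uses only participants with a final score.

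With *a* missing in the worse arm and *b* in the other, and the same *d* in both:
- shift towards zero: *s* = (*a* − *b*)/60 × *d*
- SE = 1.81 × √(1/(60 − *a*) + 1/(60 − *b*))
- P(declare equivalence) ≈ Φ(*s*/SE − *t*) − Φ(−(2 − *s*)/SE + *t*), where *t* is the one-sided critical value (about 1.66 at 0.05 and 2.15 at 0.0167)

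Both levels are shown because section 6.7 uses 0.05/3 = 0.0167, while section 7.4.2 uses 0.05 unless adjusted.

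| Missing, worse arm vs other | SE | Shift for *d* = 1.5 to 3 | False equivalence at 0.05 | at 0.0167 |
|---|---|---|---|---|
| none, or equal with the same *d* | – | 0 | about 5% | about 1.5–1.6% |
| 3 vs 0 (5% read per arm, 3/60) | 0.335 | 0.075 to 0.15 | 8–11% | 3–4% |
| 6 vs 1 | 0.341 | 0.125 to 0.25 | 10–18% | 4–8% |
| 9 vs 0 (extreme) | 0.345 | 0.225 to 0.45 | 16–36% | 7–19% |

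For 6 vs 1: 5/60 × 1.5 = 0.125 and 5/60 × 3 = 0.25. With two missing in the third arm the total is 6 + 1 + 2 = 9, still not above 5% of 180. For 9 vs 0: 9/60 = 0.15, giving 0.15 × 1.5 = 0.225 and 0.15 × 3 = 0.45.

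**5. How likely the extreme is.** If missingness is unrelated to arm, the chance that all nine fall in one arm is 3 × (1/3)⁹ ≈ 0.00015.

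**6. Whether the trigger would be met.** If each of 180 participants has a 10% chance of a missing final score, P(more than 9 missing) = 98.8%. The count can fall below the trigger if early leavers are outside the FAS. If 10 of 18 dropouts left with no post-baseline efficacy assessment, FAS missingness would be 8/170 = 4.7%, although 10% were lost.

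**The case against.** Four arguments on the other side have weight.

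**Discontinuation assessments.** Section 7.8.2 asks the investigator to perform the scheduled tests when a participant discontinues, and to try to bring back those who stop attending. The endpoint runs to the end of treatment, so a BPI taken at discontinuation could be read as the final value. Participants leaving for worsening or adverse events may therefore often have a score. This stands and reduces the problem. It does not cover every loss, and the Protocol does not say whether such a score counts as the endpoint.

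**The planned dropout exceeds 5%.** At 10% dropout the trigger would usually be met if all dropouts count. This also stands, so the exact level of 5% is not the main weakness. Meeting the trigger still obliges nobody to impute.

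**Silence is not a completers-only rule.** A reader might infer that the Protocol prescribes a Visit 3 completers analysis at or below 5%, or that the 5% is counted over the whole trial. The text says neither. Both are possible readings, which is why the sizes above are conditional.

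**Detail belongs in a SAP.** Imputation models can properly be left to a SAP that is not shown, and their absence is no fault. But the Protocol itself fixes an optional, threshold-based rule, and added model detail would not make that rule a commitment.

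**Conclusion.** The point holds as a weakness of the rule. It cannot act on the primary analysis. In the only planned sensitivity analysis it is optional above 5%, silent at or below it, without a denominator, and blind to arm and reason for leaving. That suits a confirmatory equivalence comparison poorly, and it should be changed.

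The size is conditional. With leavers 1.5 to 3 points worse and a true difference at the margin, an uneven split of 6 versus 1 uses about 13–25% of the margin and raises false equivalence from about 5% to 10–18% at one-sided 0.05. Reading 5% per arm gives 0.08 to 0.15 points. Equal, non-informative dropout gives no shift. If the better arm loses its non-responders, the shift runs away from equivalence.

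A reader might take 0.45 points, or a 36% false-equivalence rate, as the expected damage. The documents do not support that. It needs all nine missing in one arm, the largest assumed gap and a true difference at the margin. The Protocol gives no leaver–completer gap; its 3-point figure is a within-patient response threshold.

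**What to change.** Replace the 5% rule with a committed FAS method that applies whatever the proportion missing. Either of these would do, with the pairwise TOST taken from it:

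- a mixed model for repeated measures on Visit 2 and Visit 3 BPI, with baseline BPI as covariate; or
- multiple imputation by arm, using baseline BPI, Visit 2 BPI and any BPI taken at discontinuation.

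State whether a discontinuation BPI counts as the end-of-treatment value. Add one delta-adjusted (tipping-point) run that worsens the imputed values in one arm at a time, and report the delta at which the equivalence conclusion changes.

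The cost is a change of wording and slightly more programming. The Visit 2 BPI is already scheduled, so no new data are needed. The FAS interval may be slightly wider than one based on completers only.

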7.11 COMPLIANCE WITH AND DEVIATION FROM PROTOCOL OR CHANGES AND REVISION OF PROTOCOL

7.11.1 Compliance with and Deviation from or Changes in Protocol

Investigator must not deviate from or change the protocol unless the Principal Investigator obtains prior written agreement with the sponsor and written approval by the institutional review board (IRB)/EC. However, this does not apply when the deviation or change is medically inevitable, for example, deviation or change for avoiding urgent risk to participants, or when the change does not affect the conduct of the study (for example, change in phone numbers).

- 1) Investigator can deviate from or change the protocol without prior written agreement with the sponsor and prior approval by the institutional review board (IRB)/EC for medically compelling reasons, for example, to avoid urgent risk to participants. In such cases, the Principal Investigator notifies the sponsor of the details of the deviation or change and its reason. The Principal Investigator also discusses the revision of the protocol with the sponsor and reaches an agreement. The approval of draft revision by the institutional review board (IRB)/EC is obtained as soon as possible.
- 2) The Principal Investigator promptly submits the report of all the changes in the study that significantly affect the conduct of the study or increase the risk to participants to the sponsor and the institutional review board (IRB)/EC.
- 3) Investigator records all the actions that deviate from the protocol. Among the actions deviate from the protocol, the Principal Investigator prepares the documents that include the reasons, immediately submits them to the sponsor, and retains a copy only for the actions for medically compelling reasons including avoidance of urgent risk to participants.

7.11.2 Revision of Protocol

The protocol and case report form are revised by the following procedures.

- 1) When the sponsor considers the revision necessary, the sponsor provides the Principal Investigator the draft revision of the protocol and case report form and other necessary materials and information.
- 2) The sponsor gives the Principal Investigator time necessary for him or her to sufficiently review the materials and information including the draft revision of the protocol provided in accordance with the previous clause and discuss with the sponsor.
- 3) After discussing with the Principal Investigator, the sponsor reaches an agreement with the Principal Investigator on the details of the revised protocol and case report form and compliance with the revised protocol. The sponsor and the Principal Investigator each sign, and date the written agreement to prove the above agreement. Similar processes are followed when the protocol and case report form are corrected at the direction of the institutional review board (IRB)/EC, within the range accepted by the sponsor.
- 4) The sponsor promptly submits the revised protocol and case report form and promptly obtains the approval by the institutional review board (IRB)/EC. For changes in the protocol related to administrative matters (for example, changes in monitors or changes in phone numbers, etc.), addition or deletion of other study sites, and changes in the Principal Investigator or other personnel at other study sites, the sponsor notifies the Principal Investigator of the details of the changes.

7.11.3 Completion or Discontinuation and Interruption of Study

7.11.3.1 Completion of Study

The completion day of the study for each subject is defined as “the day on which observation of all items specified in the protocol is completed or discontinuation day for the subject” and the completion day of the study for each study site as “the latest day among the study completion days for the participants enrolled at the study site concerned.”

After: the study treatment and observation specified in the protocol were completed for the last subject at the study site concerned, the Principal Investigator promptly notifies the institutional review board (IRB)/EC and the sponsor of the completion of the study in writing and reports the outline of the study results based on the report he or she prepared to the institutional review board (IRB)/EC and the sponsor.

7.11.3.2 Discontinuation or Interruption of Entire Study

Criteria for Discontinuation or Interruption of Entire Study

The sponsor promptly discusses the discontinuation or interruption of the study with the medical expert when the following criteria are met and continuation of the study at all the study sites is considered difficult or meaningless.

- 1) When “unexpected” serious AEs (diseases, disorders, deaths) occur
- 2) When information indicating that the tendencies in occurrence of “expected” significant AEs including number of incidents, frequency, and conditions for occurrence cannot be predicted based on the investigator’s brochure was obtained
- 3) When information indicating that the tendencies in occurrence of ADRs including number of incidents, frequency, and conditions for occurrence markedly changed for the worse was obtained
- 4) When information indicating or not indicating the superiority of the test drug to the comparator was obtained
- 5) When other information affecting the continuation of the study was obtained
 - a. Procedures for Discontinuation or Interruption of Entire Study
 - b. The entire study is discontinued or interrupted by the following procedures.
- 6) When the entire study is discontinued or interrupted, the sponsor promptly notifies all the Principal Investigators involved in the study and the regulatory agency to that effect and the detailed reasons in writing.
- 7) When the sponsor decides the discontinuation or interruption of the entire study and notifies Principal Investigators of the decision, Principal Investigators promptly notifies the institutional review boards (IRB)/EC to that effect in writing and explains the details of the discontinuation or interruption to the institutional review board (IRB)/EC.
- 8) When the Principal Investigators are notified of the discontinuation or interruption of the entire study, they promptly notify the participants receiving study treatment to that effect and take appropriate measures including switching to other therapies.

7.11.4 Discontinuation or Interruption at Study Sites

7.11.4.1 Criteria for Discontinuation or Interruption at Study Sites

When the following criteria are met, the sponsor assesses whether or not the study can be continued at all or part of the study sites.

- 1) When the protocol needs to be changed and some study sites cannot respond to the change
- 2) When the sponsor cannot approve an instruction for correction based on the opinion of the institutional review board (IRB)/EC

- 3) When the institutional review board (IRB)/EC instructed to discontinue the study
- 4) When some study sites violated GCP, the protocol, or study contract significantly or continuously

7.11.4.2 Procedures for Discontinuation or Interruption at Study Sites

The study is discontinued or interrupted at study sites by the following procedures.

- 1) When the Principal Investigator discontinued or interrupted the study, he or she promptly explains the discontinuation or interruption in detail in writing to the sponsor and the institutional review board (IRB)/EC.
- 2) When the institutional review board (IRB)/EC decided discontinuation or interruption of the study and notifies to that effect, the Principal Investigator promptly notifies the sponsor.

7.12 DIRECT ACCESS TO SOURCE DOCUMENTATION

7.12.1 Direct Access to Source Documents, etc.

The Principal Investigator accepts the monitoring and audit by the sponsor and inspection by the institutional review board (IRB)/EC and the regulatory agency and provides all the study-related records including source documents for direct access.

7.12.2 Method of Direct Access

If necessary, the study site and sponsor can have access to clinical study documents. The justification for opening access to clinical study documents will be discussed by the study site and the sponsor. Any access to clinical study documents requires prior Sponsor approval.

7.13 QUALITY CONTROL AND QUALITY ASSURANCE OF STUDY

The sponsor responsibly performs the quality assurance based on the standard operating procedures and maintains quality control system in order to assure that the study is conducted and data are generated, recorded, and reported in compliance with the protocol, the pharmaceutical affairs law, and GCP.

The sponsor will ensure that the reporting of adverse events that occur in this study will be reported to the the institutional review board (IRB)/EC and also BPOM RI in accordance with regulations applied in Indonesia.

7.13.1 Quality Control of Study

The sponsor applies quality control at each step of the handling of data in order to assure the reliability of all the study-related data and their appropriate processing.

The monitors assigned by the sponsor perform monitoring (including direct access to the study-related record such as source documents) according to the standard operating procedures and confirm that the study is being conducted appropriately at study sites in compliance with the protocol, the standard operating procedures, and Good Clinical Practice.

